6.2.3 Blinding

This is a double-blinded study as research assistants who assist participants in their assessments and the study statistician will be blinded to treatment assignment. Participants will not be blinded to group assignment. Detailed table below.

Study Staff	Blinding: Justification
Principal Investigator (PI)	Unblinded: Any AEs that occur need to be reported and reviewed. Can serve as back-up for mindfulness instructor or provider
Site Co-Principal Investigator Site Co-Principal Investigator	Unblinded: Any AEs that occur need to be reported and reviewed. At UNC one site co-PI is blinded due to involvement with EHR data and programming local REDCap
Co-Investigators (Co-I)	Blinded
Project Manager	Unblinded: Needs to interact with all staff, point of contact for AEs along with PI, randomizes participants

Study Coordinator	Not all sites have separate study coordinators-UNC only. One will be blinded and the other will be unblinded because she is the technology assistant for the intervention
Research Assistants	Blinded
Biostatistician	Blinded
Data Analyst	Blinded
Programmer	Unblinded: will need to respond to requests which may involve randomization status

6.2.4 Follow up Visits

All outcomes will be assessed at program completion and after six and twelve additional months of follow-up (eight weeks (T2), six months (T3), and twelve months (T4) from the start of the program, respectively), except satisfaction with OPTIMUM and Global Impression of Change, which will be assessed at program completion and at the six months and twelve months timepoints (T2, T3 & T4) Moreover, pain medications and healthcare utilization form will be assessed every month. Study participants will each be enrolled for up to twelve months. Follow-up for twelve months was chosen to evaluate duration of program effect on patients' cLBP.

6.2.5 Completion/Final Evaluation

Final Evaluation at twelve months (T4) will have the same assessments as at the end of the program (T2) and at six months (T3).

7. SAFETY ASSESSMENTS

We will monitor patient safety throughout 12 months of duration of the study. Potential risks of mindfulness interventions are minimal and may include the following:

- Emotional discomfort or distress may arise for some participants during exercises or at home practice related to awareness of negative emotions, thoughts, or physical sensations.
- Participants might face discomfort when sitting in a chair.
- Participants might face discomfort when doing gentle chair exercises (chair yoga)

Risks associated with mindfulness interventions are generally minimal and transient and can be managed with instructor guidance and continued experience with the practices. These risks will be explained to participants at study enrollment. An experienced mindfulness instructor will lead the sessions. Participants will be encouraged throughout the sessions to discuss their experiences with the exercises, including any emotional difficulties. Additionally, the beginning of each session will include time to discuss home practices and the participant will problem-solve with the instructor any issues that came up in practice during the week. Participants will be reminded

that the sessions are confidential in order to encourage disclosure of difficulties. For discomfort while sitting in a chair, participants will be instructed on how to be mindfully aware of discomfort and then to gently change position to one that is more comfortable.

7.1 Specification of Safety Parameters

Participants may experience discomfort in answering some of the questionnaire questions or in making disclosures in the sessions. Participants will be told that they may skip questions that they do not wish to answer and that disclosures in the program are also entirely voluntary. All patients are advised to refrain from disclosing anything said during the sessions outside the group.

7.2 Methods and Timing for Assessing, Recording, and Analyzing Safety Parameters

In the two large studies of MBSR for chronic low back pain, no significant adverse events related to the intervention were reported.^{5,6} Given that mindfulness methods take ordinary activities like sitting down, eating, lying down and walking and turn them into a meditation through directed breathing, adverse events are rare. Any adverse event reported to the MBSR instructor will be recorded, reviewed by the PIs and reported to the IRB when unexpected and study-related, and all AEs whether expected, unexpected, study related or study unrelated will be reported to the independent monitoring committee. Any adverse event that results in patient injury or requires immediate medical attention will be brought to the attention of the study team and PIs immediately. The MBSR interventionists and study team will have immediate access to the PIs through pager or cell phone number. We will collect health care system encounters every month. Any positive responses will be explored by study personnel to obtain additional information. This will then be reviewed by the PIs.

7.3 Adverse Events and Serious Adverse Events

For determining severity of an adverse event we use the following definitions (below). If a participant has an emergency department visit (but not hospitalized and discharged to home), then they are assigned of moderate intensity and if the participant is hospitalized it is assigned of serious intensity.

Adverse Event: *any untoward medical occurrence (whether physical or psychological) associated with the use of meditation or mind and body methods, or breach of confidentiality and which may have a causal relationship with the study procedures.*

Mild: Awareness of signs or symptoms, but easily tolerated; are of minor irritant type; causing no loss of time from normal activities; symptoms would not require medication or a medical evaluation; signs and symptoms are transient.

Moderate or greater severity. This adverse event requires medical evaluation and/or medical treatment; or is a serious adverse reaction.

Serious. This adverse event is fatal or life-threatening; requires hospitalization; or produces a disability.

Solicited adverse events and serious adverse events: will occur during the monthly assessments when health system utilization will be queried.

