We will obtain healthcare resource utilization directly from the EHR (Table 3). The EHR will evaluate opioids according to prescriptions written; CT/MRIs performed; invasive procedures such as injections and surgeries; outpatient primary care visits, physical therapy visits, urgent care visits, ED visits, and hospitalizations. Most utilization outcomes will be treated as count data and cumulative opioid exposure as continuous (i.e., cumulative morphine equivalents).

All 450 participants who are included based upon the screening criteria outlined above will receive identical assessments. We will use a paperless data management system that is described below. The measures are quick to administer and complete. In our experience, almost all the individual measures can be done in 5 minutes or less. The total time for assessment is expected to be 20 minutes, with many people completing measures in less time.

We will also conduct an online survey with all PCPs in the participating practice, to learn about their perspectives on how well the study procedures integrated with their work flow, overcame common barriers to chronic pain management, and were consistent with the practice's typical referral and feedback protocols. This survey will also ask PCPs to report if/how many of their patients enrolled raised safety concerns during the study, overall satisfaction with the program, and open-ended questions will solicit feedback for protocol improvements.

Outcome Measures Table (Table 2)

	T1 Baseline	T2 8-wks	*T3 6-mo	T4 12-mo	Number of Questions
Patient-reported Measures					
**PEG	X	X	X	X	3
PROMIS-29 (Q.1-4 & 17-20 same as PROMIS Physical Function & PROMIS Sleep	X	X	X	X	29
Current Opioid Misuse Measure	X	X	X	X	17
CAMS-R (mindfulness)	X	X	X	X	12
Satisfaction, single item		X	X	X	1
Ethics, single item		X			1
Patient Global Impression of Change PGIC		X	X	X	1
Opioid Use, single item	X	X	X	X	1
Pain Catastrophizing Scale Short Form	X	X	X	X	6
Demographics	X				~23
Tobacco, Alcohol, Prescription medications, and other Substance (TAPS).	X			X	5
Screening questionnaire	X				~10
Pain Medication (s) This form will be asked monthly	X	X	X	X	
Charlson Co-Morbidity Index	X				23

Health Care System Utilization (self-report). This form will be asked monthly		X	X	X	~20
HEAL-Expectation	X				6
Telehealth Usability Questionnaire	X	X			7
Total Questions OPTIMUM					(baseline) (other time points)

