7.4 Reporting Procedures

When participants report an AE or SAE a description of the AE will be recorded in REDCap and brought to the attention of the PI who will then determine if it is study related. Clinicians will make a note during the 8-week sessions, if any adverse effect comes up and report it to the study team who will record the event on the Important Medical Event Form and then notify the PI. Any unanticipated problems involving risk to subjects or others and study-related will be reported to IRB as per the University of Pittsburgh sIRB guidelines. (Refer to the “Adverse Event workflow” sheet for information on how and when to report AEs/SAEs or Unanticipated problems)

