Appendix B: Important Medical Event Form

Participant ID _____ Form Completion Date _____

Form Completed by _____ Group: _____ Arm: O1 O2 O3

DO NOT ask the questions below directly (except for #5). Allow the participant to describe the event and then ask for clarification, if needed. Fill out a separate form for each event.

1. Important medical event occurred [] Yes [] No Date of the event _____

2. Nature of the event:
[] Hospitalization
[] Emergency Room visit
[] Acute Care Visit
[] Pregnancy
[] Outpatient Procedure

Other, Specify _____

3. Description of the event and its follow up (include details in the space below):
 Injury Illness Surgery New Medication Other (specify)

4. Ask the participant: "Was this event related to your participation in the OPTIMUM study?"
 Yes No

5. Severity of the event
 Mild: required no or minimal treatment; able to carry out normal activities
 Moderate: resolved with treatment; normal activities conducted with some limitations
 Severe: required extensive medical attention; unable to carry out normal activities
 Very severe: life-threatening, disabling, fatal

6. Action taken by study staff:
 Instructed participant to contact PCP Study contacted PCP
 Instructed participant to follow MD orders Study contacted IRB and DSMB

NOTE: This form should be immediately shared with the study Project Coordinator or PI.

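### Section 7.3 defines an adverse event by exposure to meditation and possible cause, which contradicts the cause-neutral reporting in Sections 7.2 and 7.4 and Appendix B and makes AE counts non-comparable by arm

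*Combined protocol and SAP*

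**What the plan says.** Section 7.3 limits an AE to an untoward medical event linked to meditation or mind-body practice, or a confidentiality breach, "and which may have a causal relationship with the study procedures". The same section grades any emergency department visit without admission as moderate and any hospitalisation as serious, with no condition on arm or cause. It adds: "Solicited adverse events and serious adverse events: will occur during the monthly assessments when health system utilization will be queried".

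Section 7.2 says "Any adverse event reported to the MBSR instructor will be recorded" and that "all AEs whether expected, unexpected, study related or study unrelated will be reported to the independent monitoring committee". It also has encounters collected monthly, with positive answers followed up and reviewed by the PIs.

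Section 7.4 has a reported AE or SAE entered in REDCap and "brought to the attention of the PI who will then determine if it is study related". It adds a second route: clinicians note adverse effects that come up during the 8-week sessions.

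Section 6.2.2 states "All 450 participants who are included based upon the screening criteria outlined above will receive identical assessments".

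The Appendix B form lists hospitalisation, emergency room visit, acute care visit, pregnancy and outpatient procedure. It carries a field for arm and asks about relatedness as its own item. It has four severity levels, the highest being "Very severe: life-threatening, disabling, fatal".

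Under Section 9.4, one ground for stopping is harm associated with the intervention that materially changes the balance of risk and benefit.

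**The concern.** Whether something is an AE and whether the study caused it are normally two separate questions. Section 7.3 merges them and adds exposure to the intervention as a further condition. In a trial where one arm meditates and the other does not, this ties the label to the arm.

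The risk-benefit rule in Section 9.4 asks whether the intervention is associated with adverse effects. That needs a background rate from usual care, counted in the same way. If the AE listing is filtered by presumed cause, the background rate is largely filtered out and the committee cannot tell excess harm from ordinary morbidity in people with chronic pain. Section 6.2.3 leaves the PI and most site co-PIs unblinded, so possible cause would be assessed with the arm known.

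**Working it through.** There is no figure to reproduce. The check is to set the sections side by side and run some typical events through them.

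**Conditions each section places on an event**

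| Place | Depends on cause? | Depends on arm? |
|---|---|---|
| 7.3, AE definition | Yes, possible causal link required | In effect yes, through the meditation limb; the confidentiality limb is open to both arms |
| 7.3, grading of ED visits and admissions | No | No |
| 7.3, monthly solicitation | No | No |
| 7.2, reporting to the committee | No, unrelated AEs included | No |
| 7.2, instructor route | No | OPTIMUM only |
| 7.4, entry in REDCap | No, relatedness is decided afterwards | No |
| 7.4, session-clinician route | No | OPTIMUM only |
| Appendix B | No, relatedness is a separate item | No |

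The definition is the only entry that makes cause a condition of counting.

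**Hypothetical events under the literal definition**

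1. *Admission with no plausible link to the study, either arm.* It is not an AE under the definition. It is graded serious by the 7.3 rule, can be logged on Appendix B, and belongs to the unrelated class that 7.2 says will be reported. The sections disagree.
2. *ED visit for worse back pain, cause uncertain.* In OPTIMUM a link to chair exercises is conceivable, so the visit can be an AE. In usual care there is no program exposure (Section 5.1 offers OPTIMUM only at the end of participation), so the same visit is not. The asymmetry by arm comes mainly from events of this kind.
3. *Passing emotional distress, no care sought.* In OPTIMUM it may be raised in one of 8 weekly sessions and recorded. In usual care the solicited route is a query about health-system use, which is not designed to find an event that leads to no care. Section 7.3 describes mild events as needing neither medication nor medical evaluation, and most of the risks anticipated in Section 7 are of this sort.
4. *Confidentiality breach in usual care.* It can meet the definition.
5. *Distress from a questionnaire, either arm.* Section 7.1 lists this as a safety concern, yet it is not associated with meditation and falls outside the definition.

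**What remains of the unrelated class in 7.2.** Under the definition it holds only events that were thought possibly causal on entry and later found unrelated by the PI. It is narrow but not empty.

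**Severity.** Section 7.3 uses mild, moderate or greater, and serious. It places a serious reaction inside the moderate category and treats hospitalisation as an intensity. Appendix B uses mild, moderate, severe and very severe, with no seriousness field. An admission that resolves with treatment and leaves some limitation of activity is serious under 7.3 but could be moderate on Appendix B.

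**The case against.** The strongest reply is that the collection procedures do not follow the narrow sentence. All participants get the same assessments. The monthly query solicits AEs and SAEs in both arms, ED visits and admissions are graded without regard to cause, REDCap entry comes before the relatedness decision, and Appendix B is cause-neutral. On this view ordinary usual-care events are captured, and the only doubt is whether they are called AEs. This stands as far as collection goes. It does not settle the label, and Section 7.2 attaches the promise of reporting to AEs, not to encounters.

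It is also fair that extra contact is inherent in a group program compared with usual care, and that events raised in sessions should be recorded. The problem is only in pooling those events with the rest when arms are compared.

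Section 9 plans no between-arm test of AEs or SAEs. Section 9.6 compares ED visits and hospitalisations from the EHR without using the AE definition, although Table 2 restricts these to low back pain. So no planned analysis is invalidated.

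On severity, the hospitalisation box and the top Appendix B level together allow the seriousness criteria in 7.3 to be largely reconstructed. The two scales still do not map onto each other.

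**Conclusion.** The AE definition contradicts the plan's own reporting rules, and the sections must be reconciled. Followed literally, it leaves ordinary medical events in the 225 usual-care participants unlabelled as AEs. With two further reporting routes open only to OPTIMUM, AE counts by arm would not be comparable for the Section 9.4 rule. The effect is on safety monitoring and descriptive safety tables, not on the primary analysis.

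Two stronger readings are tempting and are not supported. A reader might infer that no usual-care event can ever be an AE, or that the count in that arm must be nil. The confidentiality limb is open to that arm, and several procedures collect events there without regard to cause. A reader might also infer that nothing unrelated will reach the committee. The definition asks only for a possible link, so some events can enter and later be found unrelated, and the documents do not show that the committee sees only events meeting the definition.

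No number is attached, because the documents give no event rates and any count would rest on an assumed one. The conclusion assumes that the definition is applied as written. Section 7.4 refers to an Adverse Event workflow sheet that is not in the documents, so actual handling cannot be checked.

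**What to change.** - In Section 7.3, define an AE as any untoward medical occurrence after randomisation, in either arm and regardless of cause. List a confidentiality breach as a reportable event of its own so that it is not lost.
- Record relatedness and seriousness as separate fields, completed after the event is logged, in Section 7.3 and on the Appendix B form.
- Base any by-arm AE or SAE table on the monthly query, which is common to both arms, and state that it mainly covers events leading to health care. Tabulate events raised with the instructor or session clinician separately.
- Reconcile the Section 7.3 and Appendix B severity scales so that one event receives one grade.
- Check that the Adverse Event workflow sheet agrees with the revised text.

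The cost is wording in Section 7.3, small edits to one form, and somewhat more events logged from information the monthly query already gathers. No visit, assessment or sample size changes.

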6. STUDY PROCEDURES

6.1 Schedule of Evaluations (Table 1)

Assessment	Screening & Consent	Baseline (T1)	OPTIMUM Program 1-8 weeks, End of 8 weeks (T2)	Monthly Pain Medication and Healthcare Encounters	Follow-up after 6 months (T3)	Follow-up months (T4)
Informed Consent Form	X					
Demographics		X				
Screening Questionnaire	X					
Inclusion/Exclusion Criteria	X					
Enrollment/Randomization	X					
Adverse Events			X		X	
Study Measures		X	X	X	X	

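### The only adverse event solicitation described runs through health care use, so milder distress or discomfort is actively sought mainly in OPTIMUM sessions during weeks 1–8

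*Combined protocol and SAP*

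**What the plan says.** Section 7 names the risks of the intervention. On the emotional side, "Emotional discomfort or distress may arise for some participants during exercises or at home practice". On the physical side, "Participants might face discomfort when sitting in a chair", and the same list adds gentle chair exercises. It also commits to a period: "We will monitor patient safety throughout 12 months of duration of the study".

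Section 7.3 describes one solicited mechanism: "Solicited adverse events and serious adverse events: will occur during the monthly assessments when health system utilization will be queried". Section 7.2 explains how it works: health care encounters are collected monthly, and staff look further into any positive answer. For a mild event, Section 7.3 states that "symptoms would not require medication or a medical evaluation".

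Two other staff routes are described. Events told to the mindfulness instructor are recorded (Section 7.2). Under Section 7.4, "Clinicians will make a note during the 8-week sessions, if any adverse effect comes up", they report it to the study team. Section 7.4 also has any event that a participant reports entered in the database, with no limit by arm or time.

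Table 1 in Section 6.1 has a row "Adverse Events", marked at T2 and T3 and blank in the Monthly column. It is not split by arm. Table 2 lists no adverse event item at any visit.

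**The concern.** The risks the protocol itself names are mostly of a kind that sends nobody to a clinic. A utilization query is a reasonable net for moderate and serious events and a poor one for these. The places where participants are encouraged to talk about emotional difficulties are the group sessions. Controls do not attend these during the study, and OPTIMUM participants stop attending after week 8.

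The possible distortion runs in two directions. During weeks 1–8 OPTIMUM may look worse because staff are there to hear about mild events. Afterwards, distress from any continuing home practice may look rare because the described solicitation does not reach it. Under Section 7.2 all adverse events go to the independent monitoring committee, and the first stopping criterion in Section 9.4 concerns adverse effects that change the balance of risk and benefit. The counts therefore matter even though Section 9 plans no formal comparison of adverse events.

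**Working it through.** The plan gives no figure to reproduce, and the point depends on no power or event-rate calculation. The check lists every route by which an event could be found and asks whether it would reach a mild event for which no care is sought.

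| Route | Arm | Window | Reaches a mild event without care? |
|---|---|---|---|
| Monthly utilization query (7.2, 7.3) | Both | 12 months | Not expected, by the definition of mild |
| Monthly pain medication form (Table 2) | Both | 12 months | Not expected, same reason |
| Instructor report (7.2) | OPTIMUM | Weeks 1–8, through sessions | Yes, prompted by session discussion |
| Clinician note (7.4) | OPTIMUM | Weeks 1–8 | Yes, if it comes up |
| Adverse event row at T2 and T3 (Table 1) | Both | Two visits | Unknown: no question given |
| Participant report (7.4) | Both | Any time | Only if volunteered |
| Provider survey (6.2.2) | Both | Not stated | Indirect: patient must have told the provider |
| PROMIS-29, PHQ-2, GAD-2, catastrophizing, global change (Table 2) | Both | Scheduled visits | Measures state, but no rule makes a worse score an event |

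The Important Medical Event Form (Appendix B) is not a further route. It is filled in after an event has been described, and staff are told not to put most of its questions directly.

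Reading the table by arm and period:

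- OPTIMUM, weeks 1–8: two staff routes prompted by sessions, plus volunteered reports and the T2 entry.
- Controls, weeks 1–8: volunteered reports and the T2 entry.
- Both arms after week 8: volunteered reports and the T3 entry.
- Moderate or serious events that lead to care: one solicited monthly route, the same in both arms throughout.

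Session contact thus covers 8 of about 52 weeks (8/52 ≈ 15%) in OPTIMUM and 0 weeks in controls.

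On the schedule, Section 7.3 places solicitation at the monthly assessments. Table 1 leaves the Monthly cell blank for adverse events while marking Study Measures in that column. The two need to be reconciled.

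**The case against.** The strongest reply is that the plan has more routes than Section 7.3 suggests. Table 1 schedules adverse events at T2 and T3, Section 6.2.2 says all 450 participants are assessed identically, and T3 falls after week 8. Distress is measured in both arms by several scales. Volunteered reports are accepted from anyone. This stands against any absolute claim. A reader might infer that milder harms have no solicited route at all in controls or after week 8, or that nobody asks about distress. The documents do not support either inference. What they lack is a stated question behind the T2/T3 marks and a rule linking scale scores to adverse events.

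It is also fair that Section 7.3 says when solicitation occurs and does not print its wording. The monthly form of about 20 items is not reproduced, and the adverse event workflow sheet cited in Section 7.4 is not in the documents. Either could hold more. Section 7.4 describes that sheet as guidance on how and when to report, however, which is not the same as eliciting.

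A further reply is that no between-arm analysis is planned, and that Section 7.3 ties an adverse event to mind-body practice or a confidentiality breach, so controls could hardly have one. The first part limits the consequence to counts seen by the committee and later readers. The second means that a new question alone would not be enough, and the fix allows for this.

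Finally, asking people with chronic back pain about physical discomfort every month could produce many positive answers. That stands, and it affects how the item should be worded.

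**Conclusion.** The concern holds in a limited form. As described, the plan solicits adverse events through health care use, which by its own definition would not be expected to find mild distress or discomfort. Active elicitation of those risks sits mainly in OPTIMUM sessions during weeks 1–8. Counts of milder events by arm would therefore mix unequal detection with any true difference. Capture of events that lead to care is not affected, and neither is the primary analysis.

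The size of the imbalance can be given only as contact time, about 15% of the year against none. A reader might want expected counts by arm, but the documents give neither a rate of mild events nor a capture probability, so any such figures would be invented.

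A reader might also infer from Table 1 that adverse events are not collected at T4. That does not follow. The T4 column header is damaged in the available text, and the Study Measures row also lacks a T4 mark, although Table 2 marks many measures there and Section 6.2.5 says T4 repeats the T2 and T3 assessments.

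The conclusion assumes that the unseen monthly form and workflow sheet contain no separate symptom question. If one exists, the remedy is to state it in the protocol.

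**What to change.** Add one item to the existing monthly form, worded identically in both arms: *Since your last survey, have you had new or worse emotional distress, or new or worse physical discomfort beyond your usual back pain, whether or not you sought care?*

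- Log every positive answer in both arms regardless of attribution to meditation, because the current definition would otherwise exclude most control events.
- Reconcile Table 1's Monthly cell with Section 7.3, and state what is asked at the T2 and T3 marks.
- Present adverse events by arm from this common source only, with session-reported events listed separately for OPTIMUM.

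The cost is one question on a form already sent and more mild reports to log and review. To gauge the load, assume 12 completed forms each: 450 × 12 = 5,400 forms. If 5% to 20% were positive (assumed), that is 5,400 × 0.05 = 270 to 5,400 × 0.20 = 1,080 reports. Restricting the item to discomfort beyond usual back pain is meant to keep the number low. Any remaining background should be common to both arms, so it adds noise and not unequal detection.
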